6.3.2 Clinical Response Definitions

6.3.2.1 Clinical Response at the EOT and TOC Assessments

Clinical outcome assessments (see [Table 5](#)) will be made by the Principal Investigator at the EOT and TOC visits. Clinical response will be classified as cure, failure, or indeterminate based on clinical outcome. A favourable clinical response is “clinical cure”. A clinical failure occurring at an earlier time point will be carried forward to the TOC visit.

Table 5 Clinical Response Assessments at the EOT and TOC Visits

Outcome	Definition
Clinical Cure	Total resolution of all signs and symptoms of pneumonia (ie, CABP), or improvement ^a to such an extent that further antimicrobial therapy is not necessary
Clinical Failure ^b	Any of the following: * Persistence, incomplete clinical resolution, or worsening in signs and symptoms of CABP that requires alternative antimicrobial therapy * Treatment-limiting AE leading to discontinuation of the study treatment regimen, when patient required alternative antimicrobial therapy to treat the pneumonia * Death wherein pneumonia (ie, CABP) is considered causative
Indeterminate	Study data are not available for evaluation of efficacy, for any reason including treatment change prior to completing at least 48 hours of the study treatment regimen; death wherein pneumonia is clearly non-contributory, lost to follow-up, or extenuating circumstances preclude classification as a cure or failure

^a Clinical improvement includes the absence of fever (temperature $\leq 38^{\circ}\text{C}$ oral or $\leq 38.5^{\circ}\text{C}$ rectally or tympanically) for at least 24 continuous hours, with temperature recorded twice daily, in addition to a substantial improvement in signs and symptoms of CABP. Substantial improvement includes a return to pre-CABP baseline levels for patients with decreased pulmonary function (eg, patients with chronic obstructive pulmonary disease).

^b Clinical failures at EOT are carried forward to TOC.

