12.1.1.4 Clinically Evaluable (CE) Population

The CE Population will be a subset of the MITT Population and will include patients who meet the minimal disease criteria for CABP and all evaluability criteria, including patients

who received at least the pre-specified minimal amount of the intended-dose and duration of study drug therapy, for whom sufficient information regarding the infection is available to determine the patient's outcome, and for whom there are no confounding factors that interfere with the assessment of that outcome; patients with an atypical pathogen as a sole causative pathogen of the infection will be excluded from the CE Population.

In addition to meeting the above criteria, patients must meet the following specific conditions:

- At least 48 hours of study drug therapy received in order to be considered an evaluable clinical failure, unless deemed a clinical failure based on a treatment-limiting AE
- At least 72 hours of study drug therapy received in order to be considered an evaluable clinical cure
- At least 80% of the intended doses of study drug therapy received. Compliance is determined as the total number of received doses divided by the total number of intended doses based on the first and last date and time of study drug administration
- Clinical response assessment at TOC (8 - 15 days after EOT), or a clinical failure at EOT or at any time up to 15 days after EOT is allowed. For patients who died a 28 day window up to and including 28 days after EOT is allowed
- A patient with an indeterminate response at TOC is not included in the CE population unless the reason for the indeterminate response is "Death where CABP is non causative"
- Did not receive more than one dose of an alternative (non-study) systemic antimicrobial that was potentially effective for the treatment of CABP, for a reason other than treatment failure.

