12.2.2.2 Secondary efficacy endpoints

For each secondary efficacy outcome measure listed in [Table 10](#), a two-sided 95% CI for the difference between cure, success and favourable outcome rates (ceftaroline minus ceftriaxone) will be computed using the method proposed for stratified designs by Miettinen and Nurminen ([Miettinen O et al 1985](#)). Cochran-Mantel-Haenzel weights will be used for the stratum weights (defined by district) in the calculation of the CI.

Per-Patient Clinical Cure Rate at the TOC Visit in the MITT, mMITT and ME Populations

The per-patient clinical cure rate at the TOC visit in the MITT and mMITT Populations will be determined as:

$$\frac{\text{Number of patients with outcome=clinical cure}}{(\text{Number of patients with clinical cure} + \text{Number of patients with clinical failure} + \text{Number of patients with indeterminate})}$$

By definition, patients in the ME Population must have sufficient information for the determination of clinical outcome. Thus, the per-patient clinical cure rate in the ME Population is defined as:

$$\frac{\text{Number of patients with clinical cure}}{(\text{Number of patients with clinical cure} + \text{Number of patients with clinical failure})}$$

The number and percentage of patients classified as clinical cure, clinical failure, or indeterminate (by definition, indeterminates are excluded from the ME population) will be tabulated for both treatment groups.

A two-sided 95% CI for the difference in clinical cure rates (ceftaroline minus ceftriaxone) will be computed using the method proposed for stratified designs by Miettinen and Nurminen ([Miettinen O et al 1985](#)). Cochran-Mantel-Haenzel weights will be used for the stratum weights (defined by district) in the calculation of the CI.

Per-Patient Clinical Cure Rate at the EOT Visit in the MITT and CE Populations

The per-patient clinical cure rate at the EOT visit in the MITT and CE Populations will be determined to support the findings at the TOC visit. The number and percentage of patients classified as clinical cure, clinical failure, or indeterminate (by definition, indeterminates are excluded from the CE Population) will be tabulated for both treatment groups.

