A two-sided 95% CI for the difference in clinical cure rates (ceftaroline minus ceftriaxone) will be computed using the method proposed for stratified designs by Miettinen and Nurminen ([Miettinen O et al 1985](#)). Cochran-Mantel-Haenzel weights will be used for the stratum weights (defined by district) in the calculation of the CI.

Per-Patient Microbiological Favourable Outcome Rate at the TOC Visit in the ME and mMITT Populations

Per-Patient Microbiological Response in the ME Population

This efficacy analysis will be conducted in the ME Population, which by definition excludes patients with indeterminate responses (see Section 12.1.1.5). Per-patient responses at the TOC visit will be based on per-pathogen outcomes for each pathogen isolated at baseline (see Section 6.3.4.2). Microbiological outcome categories are eradication, presumed eradication, persistence and presumed persistence, as defined in

Table 7.

Favourable microbiological outcomes are eradication or presumed eradication. Unfavourable microbiological outcomes are persistence or presumed persistence. To have an overall favourable microbiological response, the outcome for each baseline pathogen must be favourable. The proportion of patients with an overall favourable microbiological response will be defined as:

$$\frac{\text{Number of patients with eradication} + \text{Number of patients with presumed eradication}}{(\text{Number of patients with eradication} + \text{Number of patients with presumed eradication} + \text{Number of patients with persistence} + \text{Number of patients with presumed persistence})}$$

The number and percentage of patients in each treatment group recorded as having a favourable (eradication or presumed eradication) and unfavourable (persistence or presumed persistence) microbiological response will be tabulated.

A two-sided 95% CI for the difference in overall favourable microbiological response (ceftaroline minus ceftriaxone) will be computed using the method proposed for stratified designs by Miettinen and Nurminen (Miettinen O et al 1985). Cochran-Mantel-Haenzel weights will be used for the stratum weights (defined by district) in the calculation of the CI.

Per-Patient Microbiological Response in the mMITT Population

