Per-Patient Microbiological Re-infection/Recurrence Rate at the LFU Visit

This analysis will be performed in the subset of patients in the ME Population who had a favourable microbiological outcome at the TOC visit. The number and percentage of patients in each treatment group that have a re-infection or recurrence at the LFU visit will be tabulated.

Two-sided 95% CI for the difference in re-infection/recurrence rates (ceftaroline minus ceftriaxone) will be constructed using the method proposed for stratified designs by Miettinen and Nurminen (Miettinen O et al 1985). Cochran-Mantel-Haenzel weights will be used for the stratum weights (defined by district) in the calculation of the CI.

Table 10 Secondary Efficacy Endpoints

Population	Subset(s)	Assessment	Per-patient Evaluation	Outcomes
MITT, mMITT and ME		TOC	Clinical response	Cure Failure Indeterminate (MITT and mMITT)
MITT and CE		EOT	Clinical response	Cure Failure Indeterminate (MITT only)
mMITT and ME		TOC	Microbiological response	Favourable: eradication or presumed eradication Unfavourable: persistence, presumed persistence, or indeterminate (mMITT only)

Population	Subset(s)	Assessment	Per-patient Evaluation	Outcomes
MITT and CE		TOC	Overall response	Success: clinical cure and either a radiographic success or radiographic indeterminate Failure: either clinical failure or clinical indeterminate, or radiographic failure
mMITT and ME	Per pathogen	TOC	Clinical response	Cure Failure Indeterminate (mMITT only)
mMITT and ME	Per pathogen	TOC	Microbiological response	Favourable: eradication or presumed eradication Unfavourable: persistence, presumed persistence, or indeterminate (mMITT only)
CE	Clinically cured at TOC	LFU	Clinical response	Continued response Relapse
ME	Micro-biologically favourable outcome at TOC	LFU	Microbiological re-infection / recurrence	No re-infection or recurrence Re-infection or recurrence

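### Deaths not caused by CABP stay in the CE and ME populations as indeterminates, but the analysis text says those populations hold none, and the primary CE cure rate has no stated denominator

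*Protocol*

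**What the plan says.** **Which patients are in.** Table 5 (section 6.3.2.1) lists among the indeterminate outcomes "death wherein pneumonia is clearly non-contributory, lost to follow-up". Section 12.1.1.4 then says: "A patient with an indeterminate response at TOC is not included in the CE population unless the reason for the indeterminate response is" a death in which CABP is non-causative. The same section adds: "For patients who died a 28 day window up to and including 28 days after EOT is allowed". Keeping these patients is therefore deliberate. Section 12.1.1.5 defines ME as the patients who meet both the CE and the mMITT criteria, so a retained death can also be in ME.

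**What the analysis text says.** All of the following are in section 12.2.2.2.
- CE, in the EOT paragraph: "by definition, indeterminates are excluded from the CE Population".
- ME, clinical cure at TOC: "By definition, patients in the ME Population must have sufficient information for the determination of clinical outcome". The rate is cures divided by cures plus failures, and the tabulation note repeats that "by definition, indeterminates are excluded from the ME population".
- ME, microbiological response at TOC: the population is one "which by definition excludes patients with indeterminate responses", and the denominator has no indeterminate term.
- Table 10, EOT row for MITT and CE: the label reads "Indeterminate (MITT only"). The TOC clinical row limits indeterminates to MITT and mMITT.

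**What points the other way.** Table 10's overall-response row for MITT and CE at TOC classes a clinical indeterminate as a failure. The per-pathogen text in section 12.2.2.2 tabulates an indeterminate category for both mMITT and ME, while the matching Table 10 rows limit it to mMITT.

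**The primary analysis.** Section 12.2.2.1 refers to the clinical cure rate at TOC in CE and writes no denominator.

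**The concern.** A population rule and a rate formula have to agree on who is counted. Here the population rule keeps a group of deaths, and the only formula written for an evaluable population leaves them out of both numerator and denominator. Under that formula the exception in 12.1.1.4 has no effect on the rate.

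CE at TOC is the only population on which non-inferiority is concluded. An analyst who carries the ME formula over to CE drops the retained deaths. One who divides by all CE patients, or follows the overall-response row, counts them as non-cures. Dropping deaths that occur after randomisation favours whichever arm has more of them.

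**Working it through.** **Plan's own figure.** Inputs from section 12.3: cure rate 85% in both arms, margin 10%, power 90%, evaluability 77.5%. From section 12.2: two-sided 95% interval.

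n per arm = (1.960 + 1.282)² × (0.85 × 0.15 + 0.85 × 0.15) / 0.10² = 267.9, so 268 CE patients. 268 / 0.775 = 345.8, so 346 per arm and 692 in total. This reproduces the stated sample size. The denominator question leaves it unchanged.

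**Consistency of the text.**
1. A death with pneumonia non-contributory is indeterminate (Table 5).
2. That patient stays in CE (12.1.1.4) and, with a qualifying pathogen, in ME (12.1.1.5).
3. ME is said to hold no indeterminates, and its TOC clinical denominator is cure + failure (12.2.2.2). This contradicts step 2 directly.
4. Under Table 7, such a patient with no adequate specimen is also microbiologically indeterminate, so the ME microbiological denominator has the same gap.
5. CE is said, in the EOT paragraph, to exclude indeterminates by definition. As a description of CE this contradicts step 2. In the EOT table it affects only patients who are already indeterminate at EOT; someone who dies later may be a cure or failure at EOT.
6. For CE at TOC, 12.2.2.1 gives no denominator.

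**Size of the effect.** The protocol gives no number of non-CABP deaths, so every count below is an assumption. Each arm has 268 CE members including the deaths.

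*One death:* 228/268 = 85.07%; 228/267 = 85.39%. Shift 0.32 points in that arm.

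*3 versus 0 deaths, about 85% cured among the rest:* dropped, 225/265 − 228/268 = 84.91 − 85.07 = −0.17 points. Counted, 225/268 − 228/268 = −1.12. Shift −0.95.

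*6 versus 2 deaths:* with 224 and 227 cures, dropped, 224/262 − 227/266 = +0.16. Counted, 224/268 − 227/268 = −1.12. Shift −1.28. With one cure fewer in each arm (223 and 226) the figures are +0.15, −1.12 and −1.27.

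**Effect on the decision.** The lower limit is the value d that solves (p_T − p_C − d) / √V(d) = 1.96, where V(d) is the Miettinen-Nurminen variance from the maximum-likelihood rates restricted to difference d, multiplied by N/(N − 1). The intervals are unstratified because the district-level counts needed for stratification are not available. Control has 228 cures throughout.

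| Ceftaroline cures | Deaths (ceftaroline vs ceftriaxone) | Lower limit, deaths counted | Lower limit, deaths dropped |
|---|---|---|---|
| 228 | 5 vs 5 | −6.10% | −5.89% |
| 217 | 3 vs 0 | −10.52% (fails) | −9.56% (passes) |
| 217 | 5 vs 2 | −10.52% (fails) | −9.51% (passes) |
| 217 | 5 vs 5 | −10.52% (fails) | −10.43% (fails) |

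For 3 versus 0 deaths the conclusion changes only at 216, 217 or 218 ceftaroline cures. At 215 both versions fail (−11.31% and −10.37%), and at 219 both pass (−9.72% and −8.75%).

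**The case against.** A reader might infer that the protocol gives the primary cure rate two conflicting definitions. It does not. The sentence that CE excludes indeterminates and the MITT-only label both belong to the EOT endpoint. The cure + failure formula is written only for ME. Section 12.2.2.1 is silent on the denominator, and its ordinary reading is cures over CE patients. A formula missing from a protocol can be left to the SAP that section 12.2 promises.

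A reader might also infer that the analysis text has no place for these patients in CE. That is not so either: the overall-response row of Table 10 counts a clinical indeterminate in CE as a failure.

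Nor do the documents support the idea that the denominator would be chosen knowing which arm it helps. Section 12.2 has the SAP finalised before unblinding, and section 5.4.2 keeps the codes closed until all evaluability decisions are documented.

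The numbers involved may be small. The exclusion criteria remove PORT class V, patients needing intensive care, and those with immediately life-threatening or progressively fatal disease. The MITT formula at TOC already counts these deaths as non-cures, so their effect would be visible there, although MITT does not decide non-inferiority.

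These points limit the reach and severity of the concern. They leave the contradiction standing: 12.1.1.4 and the statements in 12.2.2.2 cannot both describe CE and ME, and whichever denominator a SAP chose would still contradict part of the protocol.

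**Conclusion.** The inconsistency is real. It is explicit for ME at TOC and for the description of CE in the EOT paragraph. For the primary endpoint the defect is an unstated denominator next to an evaluable-population formula that, if borrowed, would cancel a deliberate inclusion rule.

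The likely effect is below one point to slightly above it: about 0.3 points per death in an arm, 0.95 points for 3 versus 0, and about 1.3 points for 6 versus 2, against a 10-point margin. These figures rest on 268 CE patients per arm, roughly 85% cure, unstratified intervals and assumed death counts. Balanced deaths barely move the lower limit. The decision changes only with an imbalance and a result already close to −10%. Any choice would be made before unblinding. This should be fixed, but it does not threaten the design or the sample size.

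**What to change.** - In 12.2.2.1, state that the CE clinical cure rate is clinical cures divided by all CE patients, so a retained death with CABP non-causative counts as a non-cure.
- In 12.2.2.2, use the same rule for ME: add indeterminates to the clinical denominator and to the microbiological denominator, and reword the sentence that introduces the ME clinical formula.
- Correct all three statements that indeterminates are excluded by definition: the CE one under EOT, the ME one under clinical cure at TOC, and the ME one under microbiological response.
- Align the indeterminate labels in Table 10 with this rule and with the per-pathogen text, which already tabulates indeterminates for ME.

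Deleting the exception in 12.1.1.4 would also make the text consistent. Counting the deaths is preferable because it gives effect to a rule written on purpose, and it matches the MITT formula and the overall-response row.

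The cost is wording only, with no change to data collection or sample size. The downside is that CE and ME cure rates may come out a fraction of a point lower.

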12.1.1.5 Microbiologically Evaluable (ME) Population

The ME Population includes patients who meet criteria for both the CE (Section 12.1.1.4) and mMITT (Section 12.1.1.3) Populations.

At the TOC visit, the Principal Investigator will collect a microbiology specimen from blood, sputum, and pleural fluid samples only if medically indicated. Hence, many or most patients will not have a TOC microbiology specimen available for analysis. If a suitable specimen cannot be collected, the per-pathogen microbiological outcome will be "presumed eradicated" or "presumed persistent" based on the clinical response.

12.1.2 Safety analysis set

The MITT population will be used to summarise safety data, ie, patients who received at least one dose of randomised investigational product, (ceftaroline fosamil, ceftriaxone) and for whom any post-dose data are available. Throughout the safety results sections, erroneously

treated patients (eg, those randomised to treatment ceftaroline fosamil but actually received ceftriaxone) will be accounted for in the actual treatment group received.

12.2 Methods of statistical analyses

Inferential statistical analyses as specified will be conducted and all comparisons will be between the ceftaroline and ceftriaxone groups. Two-sided 95% confidence intervals will be constructed for assessment of non-inferiority and a two-sided alpha level of 0.05 will be used for significance; no adjustment will be made for multiple comparisons. Descriptive statistics, including the numbers and percentages for categorical variables, and the numbers, means, standard deviations, medians, minimums and maximums for continuous variables will be provided. Listings of individual patients' data will also be produced. A comprehensive SAP will be prepared and finalized prior to unblinding and analysis of the data.

12.2.1 Analysis of study population and patient characteristics

Enrolment, protocol deviations, and discontinuations from the study will be summarized by treatment group. Protocol deviations are defined as any variation from the protocol including enrolment of a patient who did not meet all inclusion and exclusion criteria, and failure to perform the assessments and procedures within the required time frame. Important deviations will be summarised by treatment group.

Demographics (age, race, gender), medical and surgical history, PORT Risk Class, baseline assessment of the clinical symptoms and signs of CABP, microbiological assessment of blood, sputum, and pleural fluid specimens, and administration of study treatment will also be summarized.

12.2.2 Efficacy analyses

12.2.2.1 Primary efficacy endpoints

The primary objective of this study is to determine the non-inferiority in the clinical cure rate for ceftaroline compared to that for ceftriaxone at the TOC visit in the CE Population in adult patients with CABP. A two-sided 95% confidence interval (CI) for the observed difference in the cure rate (ceftaroline group minus ceftriaxone group) will be computed using the method proposed for stratified designs by Miettinen and Nurminen ([Miettinen O et al 1985](#)). Cochran-Mantel-Haenzel weights will be used for the stratum weights (defined by district) in the calculation of the CI. This method corresponds to the expanded Farrington-Manning test ([Farrington CP and Manning G 1990](#)) for stratified designs with Cochran-Mantel-Haenzel weights. Non-inferiority of ceftaroline will be concluded if the lower limit of the 95% CI is -10% or higher.

If the clinical cure rates for ceftaroline are higher than that seen in ceftriaxone group and non-inferiority has been established in CE Population, a test of superiority will be conducted in the CE and MITT populations. Superiority of ceftaroline will be concluded if the two-sided p-value is less than 0.05.

An additional assessment of the treatment group-by-district interaction on the primary efficacy outcome measure will be performed descriptively. The primary efficacy measure will be summarised by treatment group and district.

12.2.2.2 Secondary efficacy endpoints

For each secondary efficacy outcome measure listed in [Table 10](#), a two-sided 95% CI for the difference between cure, success and favourable outcome rates (ceftaroline minus ceftriaxone) will be computed using the method proposed for stratified designs by Miettinen and Nurminen ([Miettinen O et al 1985](#)). Cochran-Mantel-Haenzel weights will be used for the stratum weights (defined by district) in the calculation of the CI.

Per-Patient Clinical Cure Rate at the TOC Visit in the MITT, mMITT and ME Populations

The per-patient clinical cure rate at the TOC visit in the MITT and mMITT Populations will be determined as:

$$\frac{\text{Number of patients with outcome=clinical cure}}{(\text{Number of patients with clinical cure} + \text{Number of patients with clinical failure} + \text{Number of patients with indeterminate})}$$

By definition, patients in the ME Population must have sufficient information for the determination of clinical outcome. Thus, the per-patient clinical cure rate in the ME Population is defined as:

$$\frac{\text{Number of patients with clinical cure}}{(\text{Number of patients with clinical cure} + \text{Number of patients with clinical failure})}$$

The number and percentage of patients classified as clinical cure, clinical failure, or indeterminate (by definition, indeterminates are excluded from the ME population) will be tabulated for both treatment groups.

A two-sided 95% CI for the difference in clinical cure rates (ceftaroline minus ceftriaxone) will be computed using the method proposed for stratified designs by Miettinen and Nurminen ([Miettinen O et al 1985](#)). Cochran-Mantel-Haenzel weights will be used for the stratum weights (defined by district) in the calculation of the CI.

Per-Patient Clinical Cure Rate at the EOT Visit in the MITT and CE Populations

The per-patient clinical cure rate at the EOT visit in the MITT and CE Populations will be determined to support the findings at the TOC visit. The number and percentage of patients classified as clinical cure, clinical failure, or indeterminate (by definition, indeterminates are excluded from the CE Population) will be tabulated for both treatment groups.

A two-sided 95% CI for the difference in clinical cure rates (ceftaroline minus ceftriaxone) will be computed using the method proposed for stratified designs by Miettinen and Nurminen ([Miettinen O et al 1985](#)). Cochran-Mantel-Haenzel weights will be used for the stratum weights (defined by district) in the calculation of the CI.

Per-Patient Microbiological Favourable Outcome Rate at the TOC Visit in the ME and mMITT Populations

Per-Patient Microbiological Response in the ME Population

This efficacy analysis will be conducted in the ME Population, which by definition excludes patients with indeterminate responses (see Section 12.1.1.5). Per-patient responses at the TOC visit will be based on per-pathogen outcomes for each pathogen isolated at baseline (see Section 6.3.4.2). Microbiological outcome categories are eradication, presumed eradication, persistence and presumed persistence, as defined in

Table 7.

Favourable microbiological outcomes are eradication or presumed eradication. Unfavourable microbiological outcomes are persistence or presumed persistence. To have an overall favourable microbiological response, the outcome for each baseline pathogen must be favourable. The proportion of patients with an overall favourable microbiological response will be defined as:

$$\frac{\text{Number of patients with eradication} + \text{Number of patients with presumed eradication}}{(\text{Number of patients with eradication} + \text{Number of patients with presumed eradication} + \text{Number of patients with persistence} + \text{Number of patients with presumed persistence})}$$

The number and percentage of patients in each treatment group recorded as having a favourable (eradication or presumed eradication) and unfavourable (persistence or presumed persistence) microbiological response will be tabulated.

A two-sided 95% CI for the difference in overall favourable microbiological response (ceftaroline minus ceftriaxone) will be computed using the method proposed for stratified designs by Miettinen and Nurminen (Miettinen O et al 1985). Cochran-Mantel-Haenzel weights will be used for the stratum weights (defined by district) in the calculation of the CI.

Per-Patient Microbiological Response in the mMITT Population

This analysis will be used to support the favourable outcome of microbiological response (eradication or presumed eradication) in the ME Population. The microbiological response for the mMITT Population will be reported at the TOC visit. Per-patient responses will be based on per-pathogen outcomes for each pathogen isolated at baseline (see Section 6.3.4.2). Microbiological outcome categories are eradication, presumed eradication, persistence and presumed persistence, as defined in

Table 7.

Favourable microbiological outcomes are eradication or presumed eradication. Unfavourable microbiological outcomes are persistence or presumed persistence. To have an overall favourable microbiological response, the outcome for each baseline pathogen must be favourable. If the only outcome available is indeterminate (or both EOT and TOC assessments

are missing), the final outcome for the patient will be considered indeterminate. Superinfections will not be considered in the microbiological response. The proportion of patients with an overall favourable microbiological response will be defined as:

$$\frac{\text{Number of patients with eradication} + \text{Number of patients with presumed eradication}}{\text{(Number of patients with eradication} + \text{Number of patients with presumed eradication} + \text{Number of patients with persistence} + \text{Number of patients with presumed persistence} + \text{Number of patients with Indeterminate})}$$

The number and percentage of patients with favourable responses (eradication or presumed eradication), unfavourable (persistence or presumed persistence) or indeterminate will be tabulated for both treatment groups.

A two-sided 95% CI for the difference in overall favourable microbiological response (ceftaroline minus ceftriaxone) will be computed using the method proposed for stratified designs by Miettinen and Nurminen (Miettinen O et al 1985). Cochran-Mantel-Haenzel weights will be used for the stratum weights (defined by district) in the calculation of the CI.

Per-Patient Overall Success Rate at the TOC Visit in the CE and MITT Populations

The overall response will be assessed programmatically by combining the clinical response with the radiographic response. To be an overall success the patient must be deemed a clinical cure and either a radiographic success or radiographic indeterminate.

The per-patient overall success rate at the TOC visit in the CE and MITT Populations will be determined. The number and percentage of patients classified as overall success or overall failure will be tabulated for both treatment groups.

Two-sided 95% CI for the difference in overall response rates (ceftaroline minus ceftriaxone) will be constructed using the method proposed for stratified designs by Miettinen and Nurminen (Miettinen O et al 1985). Cochran-Mantel-Haenzel weights will be used for the stratum weights (defined by district) in the calculation of the CI.

Per-Pathogen Clinical Cure Rate and Microbiological Success Rate at the TOC Visit in the mMITT and ME Populations

Clinical response by baseline pathogen will be determined as the proportion of patients with a clinical cure for each pathogen isolated at baseline. The number and percentage of mMITT and ME Populations in each treatment group recorded as a clinical cure, clinical failure, and indeterminate (see Section 6.3.2) will be tabulated per baseline pathogen. Two-sided 95% CIs for the difference in clinical cure rate per baseline pathogen will be derived where deemed appropriate.

Microbiological response by baseline pathogen will be determined as the proportion of patients with a favourable microbiological response (eradication or presumed eradication) for each pathogen isolated at baseline. The number and percentage of mMITT and ME Populations in each treatment group recorded as having a microbiologically favourable (eradication or

presumed eradication), unfavourable (persistence or presumed persistence), or indeterminate outcome (see Section 6.3.4.1) will be tabulated per baseline pathogen. Two-sided 95% CIs for the difference in microbiological response rate per baseline pathogen will be derived where deemed appropriate.

Per-Patient Clinical Relapse Rate at the LFU Visit

This analysis will be performed in the subset of patients in the CE Population who were a clinical cure at the TOC visit. The number and percentage of patients in each treatment group that have relapsed at the LFU visit will be tabulated.

Two-sided 95% CI for the difference in relapse rates (ceftaroline minus ceftriaxone) will be constructed using the method proposed for stratified designs by Miettinen and Nurminen (Miettinen O et al 1985). Cochran-Mantel-Haenzel weights will be used for the stratum weights (defined by district) in the calculation of the CI.

Per-Patient Microbiological Re-infection/Recurrence Rate at the LFU Visit

This analysis will be performed in the subset of patients in the ME Population who had a favourable microbiological outcome at the TOC visit. The number and percentage of patients in each treatment group that have a re-infection or recurrence at the LFU visit will be tabulated.

Two-sided 95% CI for the difference in re-infection/recurrence rates (ceftaroline minus ceftriaxone) will be constructed using the method proposed for stratified designs by Miettinen and Nurminen (Miettinen O et al 1985). Cochran-Mantel-Haenzel weights will be used for the stratum weights (defined by district) in the calculation of the CI.

Table 10 Secondary Efficacy Endpoints

Population	Subset(s)	Assessment	Per-patient Evaluation	Outcomes
MITT, mMITT and ME		TOC	Clinical response	Cure Failure Indeterminate (MITT and mMITT)
MITT and CE		EOT	Clinical response	Cure Failure Indeterminate (MITT only)
mMITT and ME		TOC	Microbiological response	Favourable: eradication or presumed eradication Unfavourable: persistence, presumed persistence, or indeterminate (mMITT only)

Population	Subset(s)	Assessment	Per-patient Evaluation	Outcomes
MITT and CE		TOC	Overall response	Success: clinical cure and either a radiographic success or radiographic indeterminate Failure: either clinical failure or clinical indeterminate, or radiographic failure
mMITT and ME	Per pathogen	TOC	Clinical response	Cure Failure Indeterminate (mMITT only)
mMITT and ME	Per pathogen	TOC	Microbiological response	Favourable: eradication or presumed eradication Unfavourable: persistence, presumed persistence, or indeterminate (mMITT only)
CE	Clinically cured at TOC	LFU	Clinical response	Continued response Relapse
ME	Micro-biologically favourable outcome at TOC	LFU	Microbiological re-infection / recurrence	No re-infection or recurrence Re-infection or recurrence

